2.0 Change History

Version/Date	Change Log
v0.1 / 7 th March 2022	Created as new
v0.2 / 30 th March 2023	Updates based on Sponsor Feedback to SAP v0.1. Updates based on moving from Protocol v2.0 to v3.0 (and local v3.1 / v3.2). Updates to conform to the ICON SAP Template.
v0.3 / 12 th June 2023	Updates based on Sponsor Feedback to SAP v0.2.
v1.0 / 20 th June 2023	Updates based on Sponsor Feedback to SAP v0.3. Rounded version for approval of scope (ToC).
v1.1 / 7 th November 2023	Minor updates in parallel to TFL Shell creation.
v1.2 / 21 st November 2023	Updates based on Sponsor Feedback to both SAP and TFL Shells v1.1.
v1.3 / 28 th November 2023	Minor Updates based on Sponsor Feedback to v1.2.
v1.4 / 1 st December 2023	Incorporated Sponsor request to re-derive Overall Visit Responses.
v1.5 / 15 th January 2024	Minor updates in line with Dry Run 1 production.
v1.6 / 6 th April 2024	Minor updates based on moving to Protocol v5.0. Incorporated Sponsor feedback from Dry Run 1.
v2.0 / 8 th April 2024	Minor change to the Database Lock description. Up versioned for Final Signatures.

15.0 Appendix	
15.1 Handling of Partial Adverse Event and Medication Dates	
15.2 Coded Terms for Adverse Events of Special Interest	

4.0 Purpose

The Statistical Analysis Plan (SAP) describes the statistical methods to be used during the reporting and analyses of data collected under the Calliditas Therapeutics Suisse SA Protocol GSN000400.

5.0 Scope

The SAP outlines the following:

- Study Objectives
- Study Design
- Study Estimands
- Applicable Study Definitions
- Statistical Methods

6.0 Introduction

This SAP should be read in conjunction with the study protocol and electronic case report form (eCRF). This version of the SAP has been developed by ICON using protocol version v5.0 dated 12 December 2023 along with the local amendment for the United Kingdom (v4.2 dated 25 April 2023) and CRF v5.0 dated 19 September 2023. Any further changes to the protocol or eCRF that have an impact on the design or the planned statistical analysis will require updates to the SAP.

The initial version of the SAP will be signed prior to the biomarker interim analysis (see Section 11.0 for details). The final version of the SAP, will be issued for sponsor approval prior to the data cut off for the updated analysis (see Section 8.4 for details on the timing of database lock).

A separate Independent Data Monitoring Committee (IDMC) SAP (v1.0 dated 16 December 2022) documents the details of the regular safety and tolerability reviews performed by an unblinded IDMC.

The full set of tables, listings and figures (TLFs) described in this SAP will be produced for the primary analysis and the updated analysis. If there are patients continuing in the study after the updated analysis, a small set of adverse events (AEs), serious adverse events (SAEs) and other selected safety data listings will be updated and included in an addendum to the CSR. The full set of outputs will not be reproduced.

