8.4.3 Secondary Endpoints

The secondary endpoints are listed in Section 2.2.

An initial data cut-off will occur approximately 9 weeks after completion of enrolment, when all patients are expected to have had at least 3 cycles of pembrolizumab, at least one post-treatment scan, and the opportunity for a post-treatment tumour biopsy. At this point, the secondary endpoints (with the exception of PFS and OS) will be analysed. An updated analysis may be performed after 38 progression events have been reported. At the updated analysis, ORR, PFS, DoR, DCR, and OS will be summarised and safety data summaries will be updated as appropriate.

The key secondary endpoint of PFS will be summarised by Kaplan-Meier plots presented by treatment groups. Median PFS and the proportion of patients who are progression-free at 3, 6, and 12 months will be summarised along with 80% confidence intervals presented for each treatment group. Patients who have not progressed by the time of the data cut-off for the updated analysis will be censored. The comparison between the treatment groups of PFS will be performed by fitting a Cox proportional hazard model (Cox 1975) with treatment group as the only covariate. The hazard ratio for PFS, based on the profile partial likelihood from the fitted using Cox proportional hazards model, will be calculated as a measure of the treatment effect along with the respective 95% Wald confidence interval and the asymptotic p-value from the Wald test for the difference in the log hazards in the fitted model.

The secondary endpoint of OS will not be formally compared between the treatment groups but will be summarised in a Kaplan-Meier plot together with descriptive statistics, as described for PFS.

The secondary endpoints of ORR, DoR, and DCR will be summarised using descriptive statistics for each treatment group and associated 90% Agresti-Coull confidence interval.

For the key secondary endpoints of numbers of CAFs, CD8⁺ TILs, and regulatory T-cells, and the secondary endpoint of PD-L1 expression analysis in tumour tissue, it is hypothesised based on the mode of action of setanaxib that there will be a reduction in CAFs level and an increase in the number of CD8⁺ TILs. Data will be summarised

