8.4 Database Lock

The data cut off for the updated analysis (or primary analysis if the updated analysis is not performed due to close proximity to the primary), will also be the final database lock, as long as there are no patients remaining on treatment at the time of the data cut off. If patients remain on treatment after this data cut off, then an interim lock will be used for the primary analysis and the final database lock will occur once all patients have completed study treatment or withdrawn from the study. An updated safety analysis will be performed if the final database lock occurs after the interim lock. Full details of the primary and updated analyses are given in Section 12.5.

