12.5 Efficacy Analyses

The data cut-off for the primary analysis will occur approximately 15 weeks after completion of enrolment, when all patients are expected to have had at least 5 cycles of pembrolizumab, at least two post-treatment scans, and the opportunity for a post-treatment tumour biopsy. This analysis will include the primary endpoint of best percentage change in tumour size and all secondary endpoints (excluding Cox proportional hazards for PFS) will be analysed. Investigators and patients will continue to be blinded to randomised study treatment after initial unblinding of data for the primary analysis until the final database lock.

An updated analysis may be performed after approximately 38 progression events have been reported. This updated analysis will include only the secondary endpoints of PFS, and OS in addition to an updated waterfall plot for the primary endpoint of best percentage change in tumour size.

During ongoing review of the overall progression event count, if the predicted timing of the initial and updated analyses are expected to be close in proximity, one analysis may be performed.

Efficacy analyses will be conducted using the FAS. To understand the robustness of the results from important protocol deviations, the primary efficacy analyses will also be performed using the PPS.

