12.6 Safety Analyses

Safety analyses will be conducted using the Safety Analysis Set and will be summarised descriptively, unless otherwise noted in the sections that follow. All safety related outputs will be produced at the time of both the primary analysis and the updated analysis (see Section 12.5).

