12.6.1 Adverse Events

All AEs recorded in the eCRFs will be coded using MedDRA (version 25.0 or higher) and graded using the National Cancer Institute (NCI) Common Terminology Criteria for Adverse Events (CTCAE) v5.0. Events that are not coded at the time of a data snapshot will be included and presented using the verbatim term (in uppercase letters) as the PT and "UNCODED" for the SOC. Events with missing severity at the time of the data snapshot will be left as missing.

Summary tables will present the number of events reported as well as the number and percentage of patients reporting them, unless otherwise specified.

An overall summary of TEAEs, will be provided, including line items for the following;

- TEAEs
- Severe (CTCAE Grade ≥3) TEAEs
- TEAEs Related to IMP
- TEAEs with a Fatal Outcome
- TEAEs of Special Interest (see Section 10.10.5)
- Serious TEAEs
- Serious TEAEs Related to IMP
- TEAEs Leading to a Reduction of the IMP Dose
- TEAEs Leading to the Discontinuation of IMP (Drug Withdrawal)
- TEAEs Leading to Discontinuation from the Study

A summary of TEAEs by SOC, PT and maximum severity will also be presented by patient (not events). Patients who experience multiple events within the same SOC/PT will be counted only once in the most severe grade.

The following types of TEAEs will also be summarised by SOC and PT:

- TEAEs
- Severe (CTCAE Grade ≥3) TEAEs
- TEAEs Related to IMP
- TEAEs of Special Interest
- TEAEs Leading to the Discontinuation of IMP (Drug Withdrawal)

• TEAEs Leading to Discontinuation from the Study

TEAEs will also be summarised by PT only.

All AEs (including non-TEAEs) will be listed and any AE occurring after a patient has received another anti-cancer therapy (after discontinuation of study treatment) will be flagged.

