12.6.3 Laboratory Data

Central laboratory data (haematology, serum chemistry, thyroid function) and local laboratory data (urinalysis) will be converted to Système International (SI) units. Any results containing the character values of "<" or ">" will be converted to the equivalent lower/upper limit of quantification (LLQ/ULQ). For each laboratory category and parameter noted in Table 4, absolute and change from baseline values will be summarised by analysis visit and treatment group using univariate statistics.

Shift tables of CTCAE grades from baseline to worst post-baseline will also be presented for the central laboratory data.

The change from baseline values for haematology, serum chemistry and thyroid function will be further summarised using box and whisker plots.

Standard reference ranges from the central laboratory will be used for the assessment of results being low, normal or high. Parameter results outside of the standard reference ranges will be flagged in the data listings.

Local laboratory urinalysis data will be listed only.

Table 4.	Laboratory	Parameters
----------	------------	------------

Category	Parameters			
Haematology	 Haematocrit Haemoglobin Absolute and Relative Reticulocyte Counts Red Blood Cell (RBC) Count White Blood Cell (WBC) Count Differential WBC Count 	 Platelet Count Absolute Neutrophil Count Mean Cell Volume International Normalised Ratio (INR) (Screening only). 		
Serum Chemistry	 Alkaline Phosphatase (ALP) Alanine Aminotransferase (ALT) Aspartate Aminotransferase (AST) Amylase Total and Conjugated Bilirubin Gamma-Glutamyltransferase (GGT) Glucose Total Protein 	 Albumin Creatinine Urea Total Cholesterol Triglycerides Sodium Potassium Chloride 		

Category	Parameters		
Thyroid Function	TSH and Free T4		
Urinalysis	pHProteinGlucoseKetones	 Bilirubin Blood Microscopic Examination of the Sediment 	
Pregnancy Test [†]	Serum Pregnancy TestUrine Pregnancy Test		

Note: Categories denoted with [†] will be listed only.

Note: WBC and Reticulocyte Counts will be expressed as absolute values. Differential counts will be expressed as both absolute counts and percentages of WBCs.

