12.6.5 Physical Examinations, ECGs, and Other Observations Related to Safety

The absolute values and change from baseline values of each ECG parameter (Mean Heart Rate, PR Interval, QRS duration, QT interval, RR interval (see Section 10.11) and QTcF) will be summarised using univariate statistics at each analysis visit by treatment group. The interpretation of the ECG will be presented by result category (Abnormal Clinically Significant, Abnormal Non-Clinically Significant, Normal, Unevaluable and Unknown) at each analysis visit.

The absolute and change from baseline values for QTcF intervals will be further summarised using categorical intervals (see Section 10.11). Shift tables from baseline absolute interval to the maximum post baseline interval and maximum change from baseline interval will be presented.

All 12-lead ECG data will be provided in a listing, with abnormal interpretations flagged.

All physical examination findings will be provided in a listing only.

Baseline ECOG performance status will be summarised as part of the baseline characteristics, all ECOG data will be listed. The grading of ECOG performance status is defined in Section 10.12.

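### The SAP does not say what safety analysis follows a late final lock; its only stated rule gives listings, so late events may miss the cumulative by-arm tables

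*SAP*

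**What the plan says.** Four places in the SAP bear on safety output after the last full analysis.

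- **SAP 12.6** sets the time points for the safety outputs: "All safety related outputs will be produced at the time of both the primary analysis and the updated analysis (see Section 12.5"). Final database lock is not among them.
- **SAP 6.0** covers patients who continue after the updated analysis. A small set of AEs, SAEs and "other selected safety data listings will be updated and included in an addendum to the CSR". It adds that the full outputs will not be produced again.
- **SAP 8.4** covers the same situation from the database side. If patients are still on treatment at the cut, final lock waits until all have completed or withdrawn. Then: "An updated safety analysis will be performed if the final database lock occurs after the interim lock". No content is given. The section's pointer to 12.5 covers the primary and updated analyses only.
- **SAP 12.5** allows the two analyses to be combined: "if the predicted timing of the initial and updated analyses are expected to be close in proximity, one analysis may be performed".

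The tables in question are the adverse event tables of SAP 12.6.1 ("Summary tables will present the number of events reported as well as the number and percentage of patients reporting them"), the laboratory tables of 12.6.3 ("Shift tables of CTCAE grades from baseline to worst post-baseline will also be presented for the central laboratory data") and the QTcF tables of 12.6.5 ("Shift tables from baseline absolute interval to the maximum post baseline interval and maximum change from baseline interval will be presented").

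Protocol 8.4.3 ties its own update to the updated analysis, at which "safety data summaries will be updated as appropriate".

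**The concern.** SAP 8.4 promises an analysis, SAP 6.0 supplies listings, and SAP 12.6 schedules no table at final lock. A team following the only rule with any content would issue listings. The treatment-emergent window (SAP 10.10.1) runs to 28 days after the last dose, so for every ongoing patient it extends past the cut. Events in that period would count as treatment-emergent but would not reach the by-arm counts, percentages or worst-grade shifts.

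This matters because late exposure is where the protocol sees uncertainty. Protocol 1.3 says that the higher dose and longer treatment carry a potential risk of new safety signals. Protocol 3.2 cites experience at 800 mg BID for 10 days in volunteers and at 400 mg BID for 24 weeks in patients. The preclinical signals in Protocol 1.3 (thyroid, ECG, haematology) correspond to the AESI, laboratory and QTcF tables that would not be refreshed.

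If setanaxib delays progression, the cut also leaves out a larger share of setanaxib time than of placebo time.

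**Working it through.** **1. The texts side by side.** Events between the primary and updated cuts do enter the tables, because SAP 12.6 re-runs all safety outputs at the updated analysis. Late therefore means after the last full analysis. From then on, 12.6 is silent, 6.0 gives listings, and 8.4 gives an undefined analysis. If the two analyses are merged, 8.4 recognises the case but adds no content, and 6.0 speaks only of the updated analysis.

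**2. The plan's own trigger.** SAP 8.1 assumes a PFS hazard ratio of 0.5, two-sided alpha 0.20 and more than 80% power. By the Schoenfeld formula, events = 4(1.2816 + 0.8416)² / (ln 0.5)² = 18.03 / 0.4805 = 37.5, rounded up to 38. Power at 38 events is 80.4%. The figure reproduces.

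**3. Simple bounds, both arms together.** Assume one event per patient and no treatment after progression. At the 38th event at most 50 − 38 = 12 of 50 (24%), or 70 − 38 = 32 of 70 (46%), could still be on treatment. If the analyses are merged at the 15-week cut, the last patient enrolled could add up to 105 + 4 − 15 = 94 weeks of treatment and safety follow-up.

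**4. Simulation of treatment time after the cut.** Inputs:
- *Long persistence*, from Protocol 3.2: on setanaxib 20/25 = 80% at 3 months, 12/25 = 48% at 6 and 8/25 = 32% at 12. Monthly hazards are −ln(0.80)/3 = 0.074, −ln(0.48/0.80)/3 = 0.170 and −ln(0.32/0.48)/6 = 0.068, the last carried on to the 24-month cap. The median is just under 6 months.
- *Short persistence*: the lower end of the 3 to 6 month median in Protocol 1.3. An exponential shape is assumed, with hazard ln 2/3 = 0.231 per month.
- Placebo hazard equal to setanaxib, or doubled (PFS hazard ratio 0.5).
- 0% or 20% of patients stop IMP early (assumed).
- Uniform enrolment over 12 to 36 months (assumed; the documents give no enrolment time).
- Cut: the later of the 38th event and 15 weeks after the last patient is enrolled.

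| Persistence | N | Setanaxib patients on IMP at cut (mean) | Setanaxib time after cut |
|---|---|---|---|
| Long | 50 | 3.8 to 8.6 of 25 | 13.3% to 30.2% |
| Long | 70 | 5.9 to 14.6 of 35 | 15.0% to 39.5% |
| Short | 50 | about 1.4 to 4.0 of 25 | about 6% to 16% |
| Short | 70 | about 1.8 to 5.5 of 35 | about 5.5% to 15.5% |

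The share falls as enrolment lengthens at N=70. With long persistence it is 36.6% to 39.5% at 12 months, 21.9% to 23.1% at 24 and 15.0% to 15.7% at 36. With short persistence, N=50 and 36 months of enrolment, nobody on setanaxib remained at the cut in 18% to 25% of runs.

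**5. Balance between arms.** With the hazard ratio at 0.5, N=50 and long persistence, the share after the cut is 15.0% to 30.2% on setanaxib against 7.9% to 14.5% on placebo. Patients still on IMP are 4.2 to 8.6 against 1.7 to 3.2.

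**6. Merged analysis.** With N=70 and long persistence, the 38th event fell before, or within a month after, the 15-week cut in 93% to 100% of runs. A single analysis is then the likely case.

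**The case against.** The strongest reply is that SAP 6.0 and 8.4 can be read together. Section 8.4 commits without qualification to an updated safety analysis, and declining to reproduce the full set does not forbid a partial set of tables. This stands: the documents do not establish that late events will be left out, only that nothing says they will be put in.

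Second, listings in a CSR addendum are an openly stated choice for a small residual group in a proof-of-concept study with descriptive safety. Late AEs and SAEs still reach the reader, and AESIs are still reported within 24 hours. That limits the harm, but a listing does not give by-arm incidence or worst-grade shifts over the whole treatment period.

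Third, the IDMC sees unblinded data, and its outputs are specified in a separate IDMC SAP. That document, the charter, the table shells and protocol v5.0 (which the SAP cites; the protocol reviewed is v4.0) were not available, so nothing can be said about by-arm tables there.

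A reader might infer three stronger things that the documents do not support.
- *That the SAP departs from the protocol.* Protocol 8.4.6 asks for by-arm summaries without naming a cut, but 8.4.3 places the safety update at the updated analysis, and SAP 12.6 delivers it there.
- *That late safety data are dropped.* They are listed.
- *That 30% or 40% of events would be missed.* The percentages measure treatment time, and the 40% needs long persistence with 70 patients enrolled in 12 months.

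**Conclusion.** The point holds as an inconsistency with a practical consequence. SAP 6.0 and 12.6 do not align with 8.4. Under the only rule that has content, events and worsening after the last full cut stay outside the cumulative by-arm tables. It is more than a missing cross-reference, because 6.0 states a rule that serves the safety objective less well than a cheap alternative. It is an improvement worth making and does not invalidate the plan.

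Across both persistence cases, about 1 to 9 of 25 setanaxib patients (N=50) or 2 to 15 of 35 (N=70) would still be on IMP at the cut. About 6% to 30%, or 6% to 40%, of setanaxib treatment time would follow it. At a PFS hazard ratio of 0.5 the share is larger on setanaxib than on placebo. These ranges rest on the assumed enrolment time, the assumed shape of the short-persistence curve, and treatment ending at progression unless stopped earlier. If no patient remains on treatment at the cut, the gap does not arise.

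**What to change.** In SAP 6.0, replace the last two sentences with wording such as:

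> If final database lock is later than the updated (or merged) analysis, the selected AE, SAE and safety listings will be updated, and the existing exposure, TEAE, serious TEAE, AESI, laboratory CTCAE shift and QTcF shift tables will be re-run once, cumulatively on all data, by treatment group. Both will be included in the CSR addendum. Crude percentages will be read beside the exposure table, because treatment duration may differ by arm. Other outputs will not be reproduced.

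In SAP 8.4, define the updated safety analysis by reference to Section 6.0. In SAP 12.6, add final database lock, if later, as a time point for the tables named in 6.0.

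The cost is one extra run and check of programs already validated, with no new data or visits. The downside is that the re-run crude percentages will reflect unequal exposure if setanaxib patients stay on treatment longer, which is why the wording ties them to the exposure table.

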6.1 Changes from Protocol

6.1.1 Major Changes

• Initial Data Cut-Off for Primary Analysis

Section 8.1 of the protocol states the *"initial data cut-off will occur approximately 9 weeks after completion of enrolment, when all patients are expected to have had at least 3 cycles of pembrolizumab, at least one post-treatment scan, and the opportunity for a post-treatment tumour biopsy."*. During the preparation of this SAP a decision was made to extend this to approximately 15 weeks after completion of enrolment, with the aim for patients to have at least two post-treatment scans. This is clarified in Section 12.5 of this SAP.

Inclusion of the HPV Stratification Factor in Modelling

Section 8.4.2 of the protocol states the fitted analysis of covariance (ANCOVA) model as the only method to analyse the primary efficacy endpoint and without reference to human papillomavirus (HPV) status as a possible covariate. HPV status has been used as the stratification factor in the design of the study and not accounting for this factor in the analysis model may enhance the unexplained variability in the fitted linear model. Therefore, the HPV status will be included as a covariate in the ANCOVA model, if there are at least 10 patients at each level within each treatment group.

The same approach has been taken for the analysis of the cancer-associated fibroblasts (CAFs), cluster of differentiation 8 (CD8⁺), tumour-infiltrating lymphocytes (TILs) and the programmed cell death ligand 1 (PD-L1) expressions.

The HPV stratification factor, as well as the possible treatment-covariate interaction, have also been added as predictors for the Cox proportional hazards model described in Section 10.8.1 of this SAP.

• Duration of Response (DoR)

As DoR is a time-to-event endpoint, it was decided that an analysis using the Kaplan Meier method would be more appropriate than the Confidence Interval (CI) approach for a binomial proportion. This is described in Section 12.5.4.2 of this SAP.

• Supportive Analyses

Section 8.4.5 of the protocol describes a competing risk approach, using Fine & Gray (1999) methods to further analyse PFS. It was decided during the preparation of this SAP to remove this analysis from the scope of this SAP.

• Primary Estimand

Section 8.4.2 of the protocol describes the use of a treatment policy strategy to handle intercurrent events. The treatment policy strategy allows for data to be used regardless of the presence of any intercurrent events. However as one of the listed intercurrent events is the use of alternative or additional therapy, any percentage change from baseline after this intercurrent event cannot be considered for the analysis due to an improvement being possibly related to the new therapy rather than IMP. Hence the SAP has implemented a hybrid of strategies for handling intercurrent events. This is clarified in Section 9.1.1 of this SAP.

